Extra-pelvic (Lymph Nodes)	 Retroperitoneal (including Para/Peri-Aortic R/L and Celiac axis R/L) Supradiaphragmatic (including Supraclavicular R/L, Pre/Paratracheal R/L, Posterior Mediastinal R/L, Anterior Mediastinal R/L, Subcarinal, Paracardiac R/L, Retrocrural R/L, Thoracic Hilar R/L, Mesenteric R/L, Axillary R/L, Cervical R/L)

Statistical Analysis Plan: Protocol PyL3301

Anatomic Region	CLR Lesion Locations
	Other extra-pelvic (specify, including Inguinal/Femoral R/L)
Extra-pelvic (Bone)	 Pelvic bone R/L Skull Clavicle R/L Scapula R/L Sternum Ribcage R/L Spine (including cervical/thoracic/lumbar/sacral) Extremities (including right upper, right lower, left upper, left lower) Other bone lesion
Extra-pelvic (Visceral/soft- tissue)	 Lung/pleura Liver Other visceral/soft tissue lesion (including spleen, adrenal, mediastinum, pericardium, non-nodal retroperitoneal tissue, and other visceral/soft-tissue)

Each subject will be evaluated for the primary endpoint using a single truth standard source. If a subject has more than one source, e.g., undergoes correlative imaging and needle-guided biopsy, the pathology result from the needle biopsy will be evaluated as the truth standard. If the pathology result is unevaluable or the biopsy needle is not in a positive PyL lesion, then the results of the correlative imaging will be used as the truth standard.

Subjects with positive ¹⁸F-DCFPyL PET/CT scans per local scan interpretation (detection of disease at any location) will be followed at the Efficacy visit(s) based on their ¹⁸F-DCFPyL PET/CT finding(s) (see Section 4). If a subject has a negative ¹⁸F-DCFPyL scan by the local interpretation, then no standard of truth data will be submitted by the study site and no efficacy evaluation will be performed by the central Truth Panel readers. If the subject's ¹⁸F-DCFPyL PET/CT scan is interpreted as positive by one or more of the central readers and no standard of truth data is available for evaluation, then the subject will be considered unevaluable for the primary endpoint. Please see Section 5.1.3 for subjects with positive ¹⁸F-DCFPyL scans by local interpretation where the central reader(s) identify the scan as negative.

Subjects with positive ¹⁸F-DCFPyL PET/CT scans (by central review) will be classified as TP, FP or unevaluable as presented in Table 4.

Table 4: Primary Endpoint Assessment

Composite Truth Standard Source	Truth Standard Location Result	Central PyL Reader Location Match	Subject Outcome

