In addition to presenting detection rates by anatomic region of the lesions, detection rates of any PyL positive lesion at the subject level identified by the central imaging readers will be summarized for all subjects grouped by baseline PSA values categorized as: $< 0.2 \text{ ng/mL}, 0.2 \text{ to} < 0.5 \text{ ng/mL}, 0.5 \text{ to} < 1 \text{ ng/mL}, 1 \text{ to} < 2 \text{ ng/mL}, 2 \text{ to} < 5 \text{ ng/mL} \text{ and} \ge 5 \text{ ng/mL}.$

• False Negative and True Negative Subjects

Subjects may have a positive PyL scan by local interpretation and available truth standard data, but the central readers identify the scan as negative. If this situation arises, the following rules will apply:

• If the central reader classifies the scan as negative and the truth standard is positive, then the subject will be considered a false negative

• If the central reader classifies the scan as negative and the truth standard is negative, then the subject will be considered a true negative

• True Positive Detection Rate

The overall true positive detection rate (TPR) is the rate of subjects with positive ¹⁸F-DCFPyL PET/CT scans identified by a central reader confirmed to have a positive SOT (ie, a true positive [TP] subject) divided by the total number of subjects who had a ¹⁸F-DCFPyL PET/CT scan interpreted by a central reader times 100. This represents the total fraction of true positive subjects, or TP/ (TP+FP+TN+FN), where the sum of negative PyL scans (TN+FN) are reported even if the specific breakdown of TN and FN numbers may be unknown.

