7. SAMPLE SIZE

7.1. Sample Size Justification and Calculation

The primary endpoint is the correct localization rate (CLR) at the subject level, in subjects with positive PyL PET/CT findings, defined as the percentage of subjects a one-to-one correspondence between localization of at least one lesion identified on ¹⁸F-DCFPyL PET/CT imaging and the composite truth standard. The composite truth standard is defined in Section 5.1.1

The assumed CLR of ¹⁸F-DCFPyL PET/CT imaging is 30%. Based on the varied published experience with ⁶⁸Ga-PSMA PET/CT and a meta-analysis by Perera *et al*³, approximately 76% (95% confidence interval [CI], 66-85%) of PSMA scans are positive in patients with suspected recurrence of prostate cancer following initial therapy. Therefore, in subjects with negative or equivocal findings for prostate cancer on baseline conventional imaging, 60% of subjects are conservatively estimated to have PyL PET/CT positive findings. In consideration of the extent literature for ⁶⁸Ga-PSMA PET and the present study entry criteria, approximately 30% of PSMA PET/CT positive findings may be verified by biopsy/surgery-based histopathology, conventional imaging, or PSA follow-up post-RT.⁴⁻⁷ It is therefore assumed that 30% of the positive PyL results in the study will be confirmed by the composite truth standard. If 60% of the study subjects have positive PyL scans, and 30% of these positive diagnostic scans are confirmed by the composite truth standard, the use of the PyL PET/CT will permit the detection/localization of recurrent prostate cancer in approximately 18% of the underlying target population, versus at most 5% that could be identified by conventional imaging alone.

The sample size estimates are based on the positive likelihood ratio (PLR) of CLR to prevalence.

The PLR is estimated as
$$PLR = \left(\frac{CLR}{1-CLR}\right) / \left(\frac{prevalence}{1-prevalence}\right)$$
.

Conservatively assuming the initial prevalence rate as a population parameter to be 5% by conventional imaging, ^{8,9} ⁴ if a CLR of 30% is realized, the positive likelihood ratio is expected to be 8.1, implying a considerable increase in the clinical value of PyL PET/CT to identify prostate cancer.

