8.4. Missing Efficacy Endpoints

Missing values will not be replaced for any endpoint. There should be no missing primary endpoint values for subjects with evaluable PyL scans as assessed by the central readers unless no follow-up standard of truth (SOT) was completed. The subjects will be classified as true positive, false positive, or unevaluable. If a subject undergoes PyL imaging and does not have any follow-up evaluations or if the follow-up assessments are deemed unevaluable by the central readers based on image quality or other reasons, then that subject will be considered as unevaluable.

Exploratory evaluations of the primary endpoint will be performed using multiple imputation methods to examine the impact of missing or unevaluable SOTs for subjects with positive PyL scans as interpreted by the central readers. These methods are described in detail in section 8.5.2.2.

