- The overall true positive detection rate (TPR) based on all subjects with a positive ¹⁸F-DCFPyL PET/CT regardless of positive or negative findings as assessed by the central reader, as defined in section 5.1.3. This result will be reported on the primary endpoint table.

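### The formula given for the exploratory true positive detection rate does not match its own worded definition: it drops positive scans without a usable truth standard and so overstates the rate

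*SAP*

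**What the plan says.** SAP 5.1.3 takes subjects with a centrally read positive scan and a positive truth standard, "divided by the total number of subjects who had a ¹⁸F-DCFPyL PET/CT scan interpreted by a central reader". The next sentence restates the rate as a formula: "This represents the total fraction of true positive subjects, or TP/ (TP+FP+TN+FN"). It adds how negatives are handled: "where the sum of negative PyL scans (TN+FN) are reported even if the specific breakdown of TN and FN numbers may be unknown".

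Other sections give positive scans a third possible outcome. SAP 8.4: "The subjects will be classified as true positive, false positive, or unevaluable". SAP 5.1.1, on a scan that a central reader calls positive but that has no truth data: "then the subject will be considered unevaluable for the primary endpoint". Table 4 also ends in unevaluable for an unconfirmed PSA response and for radiotherapy that did not cover all suspected lesions.

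SAP 8.5.4 describes the base differently: "The overall true positive detection rate (TPR) based on all subjects with a positive ¹⁸F-DCFPyL PET/CT regardless of positive or negative findings". That sentence goes on to cite section 5.1.3, and SAP 8.5.4 then places the result on the primary endpoint table.

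The SAP also has two false positive definitions. In 5.1.3 (False Positive Scan Rates) a false positive is a centrally positive scan that no truth standard confirms, taken over all positive scans. In 8.5.4 the percentage is one minus CLR, which rests on evaluable positives only.

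**The concern.** A proportion described in words and restated as a formula should have one denominator. Here a positive scan with no usable truth standard counts under the words but has no term in the formula, while a negative scan with no truth standard counts under both. The omission works in one direction: the numerator stays the same and the denominator shrinks.

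Unevaluable positives are expected under this design. Sites submit no truth data for locally negative scans, even when a central reader calls them positive. Protocol 4.1 discontinues subjects who have neither evaluable histology nor informative imaging and do not start locoregional radiotherapy alone within 60 days. Protocol 10.4.2 treats subjects still in follow-up at database lock as unevaluable. SAP 8.5.2.2 plans multiple imputation for such subjects.

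What is at stake is the meaning of a number printed beside the primary result. If the denominator is left open, it may be settled after the counts are known.

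**Working it through.** **Inputs (SAP 7.1).** Scanned 192; positive 60%; CLR 30%; non-evaluable 30%; CLR lower bound 20%, so half-width 0.10.

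**The plan's own figures.**
- Positive scans: 1.96² × 0.30 × 0.70 / 0.10² = 80.67, so 81, as stated.
- Scans: 80.67 / 0.60 = 134.5, stated as 134.
- Total: 134 / 0.70 = 191.4, so 192, as stated.
- Share localized: 0.60 × 0.30 = 18%, as stated.

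The documents state no expected TPR.

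**Assumption.** The plan applies the 30% to all scanned subjects and does not split it between positive and negative scans. I apply it to positive scans. This fits the plan's arithmetic, since 81 of 192 × 0.60 = 115.2 positives is 70%, but it is still an assumption, so a range follows.

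**Counts.**
- Positive: 192 × 0.60 = 115.2; negative: 76.8
- Evaluable positive: 115.2 × 0.70 = 80.6; unevaluable positive: 34.6
- TP: 80.6 × 0.30 = 24.2; FP: 56.4

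**TPR under each definition.**
- Words: 24.2 / 192 = 12.6%
- Formula: 24.2 / (24.2 + 56.4 + 76.8) = 24.2 / 157.4 = 15.4%
- Ratio: 192 / 157.4 = 1.22

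With positive rate d and unevaluable share of positives u, the ratio is 1 / (1 − d × u). It does not depend on the CLR.

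| Unevaluable share of positives (assumed) | Words | Formula | Ratio at d = 0.60 |
|---|---|---|---|
| 0% | 18.0% | 18.0% | 1.00 |
| 10% | 16.2% | 17.2% | 1 / 0.94 = 1.06 |
| 30% | 12.6% | 15.4% | 1 / 0.82 = 1.22 |
| 50% | 9.0% | 12.9% | 1 / 0.70 = 1.43 |

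**False positive percentage, same counts (30% row).** One minus CLR is 70%. Counting every unconfirmed positive gives (115.2 − 24.2) / 115.2 = 79.0%.

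**The case against.** **The words already govern.** The worded definition is the right one, and the formula reads as shorthand for it. Keeping all negatives whether or not they can be split into TN and FN also suggests that all scans were the intended base. This is a fair reading of intent. But a programmer given both could implement either, and they give different results whenever a positive scan is unevaluable.

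**The looser false positive definition would reconcile them.** If every unconfirmed positive counts as FP, as SAP 5.1.3 can be read, then TP + FP covers all positives and the formula equals the words. However, the false positive rules in SAP 5.1.1 and Table 4 require a negative finding or a location mismatch, and 8.5.4 sets the false positive percentage at one minus CLR. The reading that repairs the formula contradicts those sections.

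**The size depends on where the 30% falls.** This stands. If non-evaluable meant scans with no usable read, about 134 scans would remain, and both versions would give 134 × 0.60 × 0.30 / 134 = 18.0%.

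**Two stronger readings a reader might infer.**
- That the SAP sets three rival denominators. Taking all positive scans as the base, the wording of 8.5.4 gives 24.2 / 115.2 = 21.0%, which is 1.7 times 12.6%. But the sentence also says that negative findings are included and cites 5.1.3 for the definition. The word positive is most likely a slip, so 1.7 is not a fair measure of the problem.
- That the TPR is the planned test of the claim of "detection/localization of recurrent prostate cancer in approximately 18% of the underlying target population" against at most 5% by conventional imaging. No section makes that link or plans a comparison with 5%. The 18% applies the CLR to every positive scan, so it equals the TPR only when no positive is unevaluable.

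**Conclusion.** The definition is wrong as written and should be corrected. The words and the formula in SAP 5.1.3 differ by the number of unevaluable positive scans, and the formula always gives the higher rate when there are any. At the planning values, with 30% of positives assumed unevaluable, the excess is 2.8 percentage points. The direction is certain under the outcome classes of Table 4; the size is not, because the plan does not say what share of positives will lack usable truth data.

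The 8.5.4 sentence contradicts itself and needs repair, but as a probable slip. The two false positive definitions are a related inconsistency and should be settled at the same time.

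The consequence is limited. The TPR is exploratory, is absent from the protocol's endpoint list (Protocol 3.3), and plays no part in the success rule on the CLR lower bound. It still warrants correction because it is to be printed on the primary endpoint table.

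**What to change.** Before database lock, amend the SAP:

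1. In 5.1.3, keep the worded definition and replace the formula, for each reader, with TP / (TP + FP + unevaluable positives + all negatives).
2. In 8.5.4, describe the base as all subjects with a PET/CT interpreted by the central reader.
3. Use one false positive definition in 5.1.3 and 8.5.4. The Table 4 classification, over evaluable positives, is the one consistent with one minus CLR.
4. Print each reader's count of unevaluable positives beside the TPR on the primary endpoint table.

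The cost is SAP wording and one extra table row. No new data, visits or subjects are needed, and the primary analysis is unchanged. The reported TPR will be somewhat less favourable than the current formula would give.

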5.2. Safety Endpoints

- Incidence of treatment-emergent adverse events from time of ¹⁸F-DCFPyL dosing up to 7 (±3) days following ¹⁸F-DCFPyL dosing
- Change from Baseline to post ¹⁸F-DCFPyL injection vital signs
- Summary of concomitant medications and procedures

5.3. Pharmacokinetic Endpoints

There are no pharmacokinetic data or endpoints in this study.

6. ANALYSIS POPULATIONS

6.1. Consented Population

All subjects who sign an informed consent document will be included in the consented population.

6.2. Safety Population

The safety population includes all subjects who receive any amount of ¹⁸F-DCFPyL.

6.3. Full Analysis Set (FAS) Population

The full analysis set consists of subjects who have received any amount of ¹⁸F-DCFPyL and have ¹⁸F-DCFPyL PET/CT imaging results from at least one central reader.

6.4. Per-Protocol (PP) Population

The per protocol population consists of the FAS excluding subjects with major protocol violations. Major protocol violations will be defined prior to performing the analysis of the study following database lock. The reasons for excluding subjects from the per protocol population (PP) will be included in a subject data listing of all protocol deviations.

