9.2.2. Overdose and Underdose

For this study, any administered dose of ¹⁸F-DCFPyL differing from the prescribed dose of 9 mCi (333 MBq) by more than 20% will be considered a dosing deviation. An overdose is any administered dose greater than 10.8 mCi (400 MBq). Progenics does not recommend specific treatments for an overdose. In the event of an overdose, the subject should be monitored for any AEs for the duration of the safety reporting period. Likewise, an underdose is any administered dose less than 7.2 mCi (266 MBq). The study site should comply with the reporting requirements of their radioactive materials license and 10 CFR Part 35 - Medical Use of Byproduct Material.

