10.2.3. Per Protocol Set

The per protocol population will consist of the FAS excluding subjects with major protocol violations.

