2. INTRODUCTION

The purpose of this statistical analysis plan (SAP) is to describe the planned analyses and data displays to be included in the Clinical Study Report (CSR) for Protocol PyL-3301. This SAP was developed in accordance with ICH E9 guideline¹. All decisions regarding final analysis, as defined in this SAP document, will be made prior to database lock unless communicated to the governing Regulatory Authority. Further information can be found in the protocol.

Statistical Analysis Plan: Protocol PyL3301 October 24, 2019

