8.5.2.2. Sensitivity Analyses of the Primary Endpoint

The primary endpoint analysis will be repeated for subjects in the per-protocol analysis set, which excludes subjects with major protocol deviations.

There will also be an analysis of the primary endpoint for subjects who have positive ¹⁸F-DCFPyL scans as reported by local interpretation. These subjects will have their endpoint evaluated following the same criteria as described in Table 3. The CLR and its corresponding 95% confidence interval will be calculated in the same manner as for the three independent central PyL readers. If there are more subjects with positive PyL scans identified by the central readers than those identified by the local readers, then a population of subjects with positive scans by local read results may be used.

There will be an analysis of the primary endpoint in the full analysis set with positive ¹⁸F-DCFPyL PET/CT imaging as assessed by the central imaging readers, where the CLR lesion location recorded for pelvic lymph nodes will be grouped according to the PROMISE - standardized lymph node template² (internal iliac left, internal iliac right, external iliac left, internal iliac right, obturator left, obturator right, common iliac left, common iliac right, presacral and other pelvic lymph nodes). All other CLR lesion locations will be assessed, including laterality where applicable, as described in Table 3.

There will be an analysis of the primary endpoint in the full analysis set with positive ¹⁸F-DCFPyL PET/CT imaging as assessed by the central imaging readers, where the specific lesion location recorded on the case report form, including laterality where applicable, is used instead of the CLR lesion location as described in Table 3.

A summary table will present the number and percent of subjects with either false negative or true negative outcomes for each central imaging reader. A data listing of subjects in these endpoint categories will also be prepared.

As noted in section 8.4, pattern mixture model-based multiple imputations (MI) assuming data are missing-at-random (MAR) and tipping point analyses will be performed as sensitivity analyses to examine the influence of the missing or unevaluable SOTs for subjects who have ¹⁸F-DCFPyL PET/CT results reported by a central reader. ¹⁰ The locations of lesions as identified by the central reader(s) will be imputed as the lesion locations in the multiple imputation scenarios.

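### SAP 6.4 sets no pre-lock deadline for defining major protocol violations, which conflicts with SAP 2 and leaves the supplemental per-protocol CLR open to outcome-informed exclusions

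*SAP*

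**What the plan says.** **Timing.** SAP 6.4 (Per-Protocol Population) says "Major protocol violations will be defined prior to performing the analysis of the study following database lock". SAP 2 (Introduction) sets the general rule: "All decisions regarding final analysis, as defined in this SAP document, will be made prior to database lock unless communicated to the governing Regulatory Authority".

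**Definition.** SAP 6.4: "The per protocol population consists of the FAS excluding subjects with major protocol violations". Protocol 10.2.3 has the same definition, with no list and no timing. SAP 6.4 also requires the reasons for PP exclusion to appear in a listing.

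**Use.** SAP 8.5.2 makes the FAS the set for the primary analysis and calls the PP analysis supplemental. SAP 8.5.2.2, under sensitivity analyses, says "The primary endpoint analysis will be repeated for subjects in the per-protocol analysis set, which excludes subjects with major protocol deviations". It speaks of deviations where 6.4 speaks of violations, and neither term is defined.

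**Deviations the protocol already describes.** Protocol 9.2.2 covers any administered activity "differing from the prescribed dose of 9 mCi (333 MBq) by more than 20% will be considered a dosing deviation". Protocol 7.6 has extravasation recorded as an adverse event. Protocol 8.2.2 gives a 60-120 minute imaging window after dosing. None of the three is graded major or minor, and none is linked to the PP set.

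**The concern.** A PP repeat supports the primary result only if membership was fixed independently of outcome. SAP 6.4 is the specific rule for this decision, and it asks only that violations be defined before an analysis that itself follows lock. A statistician could follow it to the letter and write the list with the locked data at hand.

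By then each subject's central reads, histopathology, correlative imaging and PSA results are in the database, and true-positive (TP) or false-positive (FP) status follows from them. Treatment is open-label, there is one arm, and no provision requires violations to be assigned without sight of those results. At stake is the credibility of one prespecified sensitivity analysis of the primary endpoint.

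**Working it through.** **1. The two timing rules side by side**

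| Source | Deadline stated | Exception |
|---|---|---|
| SAP 2 | before database lock | decisions communicated to the regulator |
| SAP 6.4 | before the analysis, which follows lock | none stated |

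Whether the closing words of 6.4 attach to the defining or to the analysis, the sentence contains no pre-lock deadline. A definition made before lock satisfies both sections. A definition made after lock and before the analysis satisfies 6.4, but breaches SAP 2 unless the regulator is told.

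**2. Which sets are affected**

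- Safety (SAP 6.2): dosed subjects, whatever amount was given. Off-dose subjects are in by rule.
- FAS (SAP 6.3): "The full analysis set consists of subjects who have received any amount of" the agent and have a result from at least one central reader. Off-dose subjects with a read are in by rule.
- PP (SAP 6.4): depends on the undefined list, so this is the only set left open.

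**3. The planned number**

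Inputs from SAP 7.1: CLR 0.30, lower limit 0.20 (half-width 0.10), two-sided 95% normal approximation.

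n = 1.96² × 0.30 × 0.70 / 0.10² = 80.67, rounded up to 81, as stated.

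**4. How far a few exclusions move a borderline reader**

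Lower limit = p − 1.96 × √(p(1 − p)/n), the interval of SAP 8.5.2.1. The 0.20 bound is the primary success threshold and serves here only as a yardstick, because no success rule is set for PP. I assume 81 evaluable positive subjects for one reader. The documents give no count of likely exclusions, so one and two are assumptions.

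| TP/n | p | Lower limit | Against 0.20 |
|---|---|---|---|
| 24/81 | 0.2963 | 0.1969 | below |
| 24/80 (one FP dropped) | 0.3000 | 0.1996 | below |
| 24/79 (two FP dropped) | 0.3038 | 0.2024 | above |
| 25/81 | 0.3086 | 0.2080 | above |
| 24/80 (one TP dropped from 25/81) | 0.3000 | 0.1996 | below |

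With 81 subjects, 25 TP is the smallest count that clears 0.20. Two exclusions are 2/81 = 2.5% of the set. Away from this boundary, one or two exclusions do not cross the line: 22/81 gives 0.175, and 22/79 still gives only 0.180.

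**The case against.** The strongest reply is that SAP 2 covers every final-analysis decision and so supplies the deadline that 6.4 omits. On that view 6.4 is loosely drafted and gives no permission to decide late. This has force: the two sections can be read together, and SAP 2 has its regulator exception. But 6.4 is the specific provision and names a later point, so the text still has to be reconciled.

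There are safeguards. PP exclusion reasons are listed (SAP 6.4), activity delivered is listed per subject (SAP 8.6.2), and CLR is tabulated by scan time, including before 60 and after 120 minutes (SAP 8.5.2.3). These would make a selective exclusion visible. They would not prevent one, and no corresponding CLR analysis exists for off-dose activity or extravasation.

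A reader might infer three stronger points that the documents do not support:

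- *That off-dose scans can be kept in or dropped from the primary analysis.* They cannot. The FAS rule keeps any dosed subject with a central read, and success is judged on the FAS for at least two of three readers.
- *That the sponsor tracks TP/FP results during the trial.* Protocol 10.4.2 describes monitoring of the number of evaluable subjects. Protocol 4.5 has sponsor representatives review listings and profiles for safety and eligibility. Knowledge of outcome at lock is possible under the wording, but it is not stated.
- *That the three described deviations must count as major.* Protocol 9.2.2 does not grade the dose deviation. Protocol 7.6 has imaging proceed after extravasation unless contraindicated for safety reasons. Protocol 4.3.2 gives the imaging window as approximate, while 8.2.2 makes it mandatory. Whether any of them counts as major is for the sponsor to decide, and the gap is that the decision is not recorded.

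**Conclusion.** The point holds for the PP set only. SAP 6.4 and SAP 2 give different deadlines for the same decision, no list of major violations exists in either document, and PP membership can be settled once outcomes are in the database. The FAS primary analysis and its success rule are unaffected.

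For a reader near the threshold, two FP exclusions or one TP exclusion would be enough to move the PP lower limit across 0.20. That rests on 81 evaluable positives, a result close to the pass mark and an assumed number of exclusions. It shows how sensitive the PP result is and does not predict what will happen. The weight is modest, because a supplemental analysis is at stake, but the correction costs almost nothing and should be made.

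**What to change.** Reconcile SAP 6.4 with SAP 2 by replacing the timing sentence in 6.4 with:

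> Major protocol violations will be defined and assigned to subjects before database lock, without reference to TP/FP outcome.

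In that pre-lock definition, state for each deviation the protocol already describes whether it counts as major for the PP set: administered activity meeting the Protocol 9.2.2 dosing-deviation definition, recorded extravasation, and PET/CT outside the 60-120 minute window. Either answer is acceptable if it is fixed in advance. For the window, first reconcile Protocol 4.3.2 with 8.2.2. Use one term, violation or deviation, in SAP 6.4 and 8.5.2.2.

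This changes no dose or imaging rule, no sample size and no primary analysis. The cost is the SAP edit and the loss of discretion after lock: a violation type recognised only later could not be used to redefine the PP set.
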